10. PROJECT TIMELINE

Quarter	Year 1				Year 2			
	1	2	3	4	1	2	3	4
Start up, Forms, IRB	■							
Recruitment & Intervention		■	■	■				
Bacterial DNA extractions and ddPCR								
Exfoliated Cell Assays, Global gene expression signatures in the exfoliome (using RNA-Seq)					■	■	■	
Plasma phospholipid PUFA								
Data Analysis and Manuscript Preparation								

11. STRENGTHS AND LIMITATIONS OF PROJECT

The strengths are: (i) translation and testing of a hypothesis in humans that has been well characterized in animal models and is supported by cogent mechanistic evidence; (ii) a robust, randomized crossover study design with within-person pairwise comparison; (iii) feeding of n-3 PUFA and prebiotic dietary fiber^{40, 41} at levels relevant to CRC prevention; (iv) pathway-based evaluation; (v) novel, non-invasive approach to measure gene expression using the stool exfoliome; (vi) targeted measures of butyrogenic potential; and (vii) extensive experience and expertise of our research team in all aspects of the proposed work. Limitations relate to the inherent challenges of short-term human dietary interventions without disease as an outcome and the R21 budget constraints. The latter limits the sample size, number of treatments (e.g., no test of n-3 PUFA and fiber individually), and comparison of exfoliome and biopsy gene expression. However, our cost-effective, robust study design, relevant dosing, and pathway-related outcomes will inform the utility of further work in this area. Further, we focus on

pathways that show, in animal models, that fish oil/fermentable fiber-containing diets protect against colon cancer by up-regulating ferroptosis/apoptosis and suppressing proliferation and inflammatory mediators.^{21, 23, 24, 87-89}

12. ANTICIPATED RESULTS, ALTERNATIVE APPROACHES AND FUTURE RESEARCH

We anticipate generating strong pilot data on the utility of n-3 PUFA + fermentable fiber to affect colonic pathways relevant to CRC prevention. With our experience in conducting human intervention studies and analyzing the proposed specimens, we do not anticipate any difficulties completing this small, pilot intervention. Furthermore, an understanding of the inter-individual differences in butyrate and n-3 PUFA disposition may inform development of tailored diet strategies for CRC-risk reduction. Specimens collected as part of this study will also be stored for additional microbiome and metabolomic analysis as future funding permits.

13. DATA SAFETY AND MONITORING PLAN

Oversight for this study will be provided by the Principal Investigators, Drs. [name] and [name] (Fred Hutch) and [name] (Texas A&M), with delegation of responsibilities to designated study personnel. They will ensure all entry criteria are met prior to the initiation of the protocol, and all study procedures and reporting of adverse events are performed according to the IRB-approved protocol.

[name], a board certified gastroenterologist at SCCA and UW Medical Center and a health services researcher with the Fred Hutchinson Institute for Cancer Outcomes Research will serve as medical advisor for the study. She will be available for consult in adverse events cases.

All adverse events related to the study procedures will be fully documented on the appropriate case report form(s) and entered in a study database. For each adverse event, the investigator will provide the onset, duration, intensity, treatment required, and outcome, including documentation of need for premature termination of any study procedures.

Anticipated adverse events related to this study are:

Blood Draws Participants may experience a little discomfort or have a temporary bruise from having blood drawn. Occasionally a participant may feel lightheaded or feel faint when having blood drawn. Blood will be taken only by trained personnel in the Fred Hutch Prevention Center Shared Resource Research Clinic using established procedures. The participants will be sitting down when the blood is drawn. If a participant feels faint, they will be instructed to lie down until the feeling goes away.

Dietary Supplements We will provide two dietary supplements during the active intervention and similar controls during the placebo periods. All participants will go through both intervention periods. Fiber: ~35 g highly-soluble, well-tolerated commercial fibers. Supplemental fiber (30-45 g/d) has been well-tolerated in short- and long-term interventions (4 wks to 1-10 y). Control: We will use maltodextrin (a food-ingredient polysaccharide made from partially hydrolysed starch) provided in the same packaging. Mild bloating and abdominal distension might occur while on the fiber treatment since the fiber content will be higher than their habitual diet. Participants will be monitored by the study staff. Most people adapt to the higher fiber intake within 3-5 days. Fish Oil: n-3 PUFA: We will provide a daily dose of 6 g EPA+DHA, consumed as 2 vials daily for 30 d. Control: We will use equivalent amounts of corn oil in visually identical packaging. Although generally safe, high amounts of EPA and DHA may thin the blood (increase clotting time) and slightly lower blood pressure. Fish oil may cause belching, bad breath, heartburn, nausea, loose stools. Participant will be instructed to report all symptoms. Study staff will contact participants after the first week on each study period to ascertain compliance and ask about any concerns they may have. Study staff will see the participants after 2 weeks provide them the needed supplements and will, again, ascertain compliance and ask about any concerns they may have. We also will maintain text and email contact with them. They fill out a daily form that includes space for commenting about symptoms or issues; thus, we are able to address the issues as they present themselves and are able to suggest ways to minimize these effects. Fish Oil - Risk of allergic

reaction will be minimized through eligibility questions addressing history of medication, food allergies / intolerances. Taking fish oil supplements with meals can often decrease gastrointestinal side effects. Participants will keep a daily study log which will include questions on health status and possible adverse experiences. A general symptom questionnaire will be administered at baseline and each subsequent visit. If there are any indications that a participant has a food allergy that was not previously known, we immediately have them stop the intervention. The study coordinator has an emergency cell phone and can be reached 24/7 by study participants.

Adverse event grading scale, based on Common Terminology Criteria for Adverse Events (CTCAE) v5.0 (Publish Date: November 27, 2017):

Grades Grade refers to the severity of the AE. The CTCAE displays Grades 1 through 5 with unique clinical descriptions of severity for each AE based on this general guideline:

Grade 1 Mild; asymptomatic or mild symptoms; clinical or diagnostic observations only; intervention not indicated.

Grade 2 Moderate; minimal, local or noninvasive intervention indicated; limiting age appropriate instrumental ADL*.

Grade 3 Severe or medically significant but not immediately life-threatening; hospitalization or prolongation of hospitalization indicated; disabling; limiting self care ADL**.

Grade 4 Life-threatening consequences; urgent intervention indicated.

Grade 5 Death related to AE.

Activities of Daily Living (ADL) *Instrumental ADL refer to preparing meals, shopping for groceries or clothes, using the telephone, managing money, etc. **Self care ADL refer to bathing, dressing and undressing, feeding self, using the toilet, taking medications, and not bedridden.

Plan for unanticipated AE reporting: All unanticipated AEs related to the study procedures that are severe or serious will be reported by [name] the IRB within 10 days of notification of the investigator. We will use as a guide the Adverse Events Relatedness Reference Sheet (Cancer Consortium Clinical Research Support) see Appendix 2. And we will follow:

Hutch IRB Policy 2.6

Adverse Biomedical Events

When, in the opinion of the principal investigator, or PI, any adverse event meets all three of the following criteria, whether they occur on- or off-site, they must be submitted to the IRB within 10 calendar days.

- **Unexpected:** An adverse event is unexpected when its nature (specificity), severity or frequency are not consistent with (a) the known or foreseeable risk of adverse events associated with the research procedures described in the protocol-related documents, such as the IRB-approved research protocol, informed consent document and other relevant sources of information such as product labeling and package inserts; and are also not consistent with (b) the characteristics of the subject population being studied, including the expected natural progression of any underlying disease, disorder or condition, or any predisposing risk-factor profile for the adverse event.
- **Related or possibly related to the research:** An adverse event is related or possibly related to research procedures if, in the opinion of the PI, it was more likely than not caused by the research procedures. Adverse events that are solely caused by an underlying disease, disorder or condition or by other circumstances unrelated to the research or any underlying disease, disorder or condition are not "related or possibly related." If there is any question whether an adverse event is related or possibly related to the research, report the adverse event.

Serious: An adverse event is serious when it results in any of the following outcomes: death, risk of death, inpatient hospitalization or prolongation of existing hospitalization, a persistent or significant disability/incapacity/or change in psychosocial status, a congenital anomaly or the requirement of an

intervention to prevent permanent impairment or damage. **Plan for anticipated AE reporting:** All serious anticipated AEs related to the study procedures will be reported by [name] to the IRB within 10 days of notification of the investigator.

Plan for ongoing review of results: The PIs will be notified within 24 hours by the research manager of any early terminations due to an adverse event.

Plan for safety review: the PI will perform a cumulative review of all adverse events and premature terminations review every 6 months after study initiation or after completion of 50% of participant visits, whichever occurs first.

Plan for annual reporting: A summary of the investigation including all adverse events and how they were handled, enrollment, drop-outs and reason for discontinuation and any protocol modifications will be provided to the IRB on an annual basis.

Annual Reports will contain:

- The number of adverse events and an explanation of how each event was handled
- The number of complaints and how each complaint was handled
- The number of subject withdrawals and an explanation of why the subject withdrew or was withdrawn
- The number of protocol deviations and how each was handled

The occurrence of any serious and unexpected event may prompt changes in study protocol. Any such change will be approved by the IRB before implementation.

Monitoring for data integrity and safety will be the responsibility of all the investigators. The following will be included:

Validity and integrity of data: Data are checked for missing, unusual, or impossible records when they are entered into the study's computer database. The investigators may consider modifications to the data-collection protocol with permission from IRB if they deem the change(s) is necessary to ensure the validity and integrity of data collected.

Enrollment rate relative to expectation: Early lags in recruitment will be rectified with increased recruitment efforts so that recruitment will be completed on time. The investigators will monitor this closely to ensure full enrollment of appropriate participants.

Retention of participants and adherence to protocol: The investigators will monitor retention and adherence to study protocol. Adherence to the study supplements will be monitored via the Daily Record that includes a calendar where participants mark daily capsules consumed.

Oversight for this study will be provided by [name] (corresponding MPI on this grant) with delegation of responsibilities to the Study Manager, [name]. They will ensure all entry criteria are met prior to the initiation of the protocol, and all study procedures and reporting of adverse events are performed according to the IRB-approved protocol. All adverse events related to the study procedures will be fully documented on the appropriate case report form(s) and entered in a study database. For each adverse event, the investigator will provide the onset, duration, intensity, treatment required, and outcome, including documentation of need for premature termination of any study procedures.

References cited

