Definite (must have all 4)	
 Has a reasonable temporal relationship to the intervention Is not readily associated with the subject's clinical state, concomitant medications/interventions, or other identifiable factors Follows a known pattern of response related to the specific intervention Disappears or decreases with reduction in dose or cessation of intervention and recurs with re-exposure (if applicable)
Probable (must have 3)	
 Has a reasonable temporal relationship to the intervention Is not readily associated with the subject's clinical state, concomitant medications/interventions, or other identifiable factors Follows a known pattern of response to intervention Disappears or decreases with reduction in dose or cessation of intervention
Possible (must have 2)	
 Has a reasonable temporal relationship to the intervention Has unknown association with the subject's clinical state, concomitant medications/interventions, or other identifiable factors Follows a known pattern of response to intervention
Unlikely (must have 2)	
 Does not have a temporal relationship to the intervention May be associated with the subject's clinical state, concomitant medications/interventions, or other identifiable factors Does not follow a known pattern of response to intervention Does not change with reduction in dose or cessation of intervention, and/or does not reappear or worsen with reintroduction of intervention (if applicable)
Unrelated (must have all 4)	
 Does not have a temporal relationship to the intervention Is associated with the subject's clinical state, concomitant medications/interventions, or other identifiable factors Does not follow a known pattern of response to intervention Does not change with reduction in dose or cessation of intervention, and/or does not reappear or worsen with reintroduction of intervention (if applicable)

This content is based in part on the National Institute of Allergy and Infectious Disease (NIAID) definitions of relatedness to adverse events.

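### The adverse event recording rule covers events judged related to study procedures, which does not match the promised reviews of all adverse events or assure an unfiltered record by treatment period

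*Combined protocol and SAP*

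**What the plan says.** Section 13 (Data Safety and Monitoring Plan) gives the recording rule in its opening paragraphs and again in its closing paragraph: "All adverse events related to the study procedures will be fully documented on the appropriate case report form(s) and entered in a study database". In both places the next sentence lists what the investigator supplies for an event: onset, duration, intensity, treatment and outcome. Relatedness is not on the list.

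Three later commitments in Section 13 carry no such limit:

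- On the safety review plan, it says: "the PI will perform a cumulative review of all adverse events and premature terminations review every 6 months after study initiation". The trigger is half of participant visits if that comes sooner.
- Plan for annual reporting: "A summary of the investigation including all adverse events and how they were handled".
- Annual report contents: the number of adverse events and how each was handled.

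On attribution, the IRB policy reproduced in Section 13 treats an event as related or possibly related if, in the PI's opinion, "it was more likely than not caused by the research procedures". It adds: "If there is any question whether an adverse event is related or possibly related to the research, report the adverse event". Appendix 2 offers a scale from Definite to Unrelated. Section 13 cites that sheet as a guide under the reporting of unanticipated events.

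On symptoms, Section 13 (Dietary Supplements) says "Participant will be instructed to report all symptoms". It describes a daily log, staff contact after the first week and again after two weeks of each period, and a symptom questionnaire at baseline and each later visit. Section 7.c provides a symptom and bowel habits questionnaire at every stool collection. Section 9.a says that questionnaire and tracking-form data will be coded and entered.

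**The concern.** The promise to use the case report form and database attaches to events already judged related. Staff who apply it literally must decide on causality before an event is written down, and an event judged unrelated has no assured place in the record. The six-monthly review and annual report are meant to cover all events, but would then draw on a source specified for a subset.

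This matters more in a randomised, double-blind crossover than in a single-arm study. Here attribution need not rest on opinion about single cases, because each participant takes both treatments and event counts on active and placebo can be set side by side. A filter based on case-level opinion weakens that comparison. It tends to favour effects that staff already expect, such as bloating or loose stools, over unlisted ones that look incidental in any one person. It also affects the IRB policy's own test: an event can count as unexpected because of its frequency, and frequency is hard to judge from counts that have already been filtered.

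**Working it through.** The plan gives no adverse event rate, safety sample size or safety analysis figure, so there is no stated number to reproduce. The check sets the passages side by side and then counts the symptom data that are collected without a filter.

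**1. Scope of each commitment**

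| Commitment | Place | Scope as worded |
|---|---|---|
| Case report form and database | Section 13, opening paragraphs | Related to study procedures |
| Same rule, repeated | Section 13, closing paragraph | Related to study procedures |
| Cumulative safety review | Section 13, Plan for safety review | All adverse events |
| Annual summary | Section 13, Plan for annual reporting | All adverse events |
| Participant symptom reports | Section 13, Dietary Supplements | All symptoms |
| Symptom questionnaire | Sections 7.c and 13; Table 1 | No relatedness limit |

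The first two rows are narrower than the next two. No section closes the gap by committing to record events whatever their attribution.

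**2. Threshold for entry.** The recording rule does not say how related an event must be. The IRB policy uses more likely than not, softened by its instruction to report doubtful cases. Appendix 2 needs only two of three listed features for Possible. Both are tied to IRB reporting, not to recording, so two staff members could apply different filters to the same event.

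**3. Symptom data collected without a filter.** Inputs: three stool collections in each of two 30-day periods (Section 4); 40 recruited, with a goal of 30 completing study measures (Section 1).

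- Questionnaires per participant: 3 × 2 = 6. Total: 6 × 30 = 180, or 6 × 40 = 240 if everyone completes.
- Leaving out the day-0 form, 2 on-treatment forms remain per period: 2 × 30 = 60 on active and 60 on placebo (80 and 80 with 40 completers).
- Daily-log days per treatment: 30 × 30 = 900 (30 × 40 = 1,200 with 40 completers).

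These counts assume that every form is returned. They show that a within-person comparison of symptoms is possible from planned data.

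**4. Whether those data fill the gap.** No section says that log or questionnaire symptoms enter the adverse event database, receive a CTCAE grade or are summarised by treatment. Table 1 gives compliance as the reason for the daily calendar and intervention effects as the reason for the questionnaire. The items on either form are not shown, so coverage beyond bowel and general symptoms is unknown. Section 13 itself names possible effects outside the gut (clotting time, blood pressure).

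**The case against.** The strongest reply is that the text promises full documentation of related events and never says that others go unrecorded. The sentence that follows the rule refers to each adverse event without qualification, and the review and annual report refer to all of them. A fair reader could conclude that broad recording is intended and the rule is loosely worded. This stands as far as intent goes. The rule is nevertheless stated twice in the same restricted form, and nothing overrides it.

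A reader might also infer that the trial cannot compare adverse effects between active and placebo. The documents do not support that. Symptoms are gathered in both periods without a relatedness test, and questionnaire and tracking data are entered. Nor can it be said that the logs lack onset, duration or intensity: their fields are not shown, and a daily log would date a symptom at least to the day.

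Three further points stand:

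- Section 9 plans no adverse event comparison and the endpoints are exfoliome mRNA profiles, so no stated analysis is lost.
- The Unlikely and Unrelated grades in Appendix 2 do not contradict the rule. Any scale used to decide relatedness needs them, and they suggest that events are noted first and attributed afterwards.
- Blinding limits filtering that differs by treatment, although symptoms that reveal the treatment could weaken this protection.

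None of these reconciles the restricted rule with the promised reviews, or links symptom data to the adverse event record.

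**Conclusion.** The point holds as a mismatch with a practical consequence. The recording rule is narrower than the reviews that depend on it. If it is followed literally, a complete, unfiltered adverse event record by treatment period is not assured. This rests on reading the rule as worded and on no other section extending it; none does.

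The documents do not allow the size to be put as a number of missed events or a bias, because they give no event rates and no attribution rates. What can be sized is the partial safeguard: 60 on-treatment questionnaires and 900 log days per treatment with 30 completers, not linked to the adverse event database. The primary endpoints and their analysis are unaffected. The change is worth making because it alters a stated rule, improves the safety data from a blinded crossover, and costs little.

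**What to change.** In both places in Section 13, replace the recording sentence with wording to this effect: *All adverse events during either intervention period or the washout, regardless of relatedness, will be documented on the case report form and entered in the study database with onset, duration, intensity, treatment and outcome. Relatedness will be graded afterwards using Appendix 2, while treatment order is still blinded.*

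Then add two statements:

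- Symptoms from daily logs and questionnaires that meet the adverse event definition are entered as adverse events. Section 13 gives a CTCAE severity scale but no general definition, so one line is needed to supply it.
- All adverse events are tabulated descriptively by the treatment of the period, with related events shown as a subset and washout events listed separately.

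The IRB reporting criteria and time limits stay unchanged. Narrowing the review and annual report to related events would also remove the inconsistency, but would leave the filter in place, so it is the weaker option.

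The cost is a wording amendment and modest extra form entry for about 40 healthy participants, whose symptoms are already being collected.
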